#### ***Pre-operative eligibility:***

##### **Subject Inclusion Criteria**

Patients who undergo immediate, implant-based reconstruction following skin-sparing mastectomy

- Patients above the age of 18, no upper age limit
- English-speaking

#### Subject Exclusion Criteria

- Patient refusal
- Patients with documented psychiatric history of psychosis or mental disorder excluding depression
- Patients who are active smokers
- Patients who will undergo any of the following:
  - Autologous tissue reconstruction
  - Combined implant and autologous tissue reconstruction
  - Patients with prior history of radiation or expected to receive post-operative radiation
  - Patients who are pregnant
  - Patients with grade III ptosis
  - Patients desiring final breast volume of greater than C cup

Following randomization preoperatively, eligibility will be determined once more intraoperatively:

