### iic. Approach

#### iib-1. Study Design

This **multi-center randomized controlled trial** will evaluate the impact of implantable human cadaveric acellular dermal matrix in the setting of immediate one-stage implant breast reconstruction. Three separate sites will participate in the trial (University Health Network, Women's College Hospital, and Vancouver General Hospital). Institutional Research Ethic Board approval has been obtained for all three sites.(APPENDIX 2) After obtaining informed consent and confirming eligibility both pre- and intra-operatively, patients will be registered in the study. Patients will be enrolled until there are 72 evaluable patients enrolled in each study arm. Stratification will be performed based on the laterality of the reconstruction (unilateral vs. bilateral reconstruction) at each of the three study sites. Patients who are deemed eligible pre-operatively by the investigating surgeon for the study will be **randomized** to undergo either **one-stage permanent prosthetic placement** with the use of implantable **acellular dermal matrix** or the conventional **two-stage TE/implant procedure** without the tissue substitute.

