#### Subject Exclusion Criteria

- Patients who undergo therapeutic or completion axillary lymph node biopsy
- Patients who have significant mastectomy flap ischemia or asymmetry between the two sides

If a completion or therapeutic axillary lymph node dissection is performed at the time of mastectomy, then the likelihood of the patient requiring postmastectomy radiation will be quite significant. It is anticipated that less than 5% of patients will be deemed ineligible on the basis of these 2 intra-operative exclusion criteria.

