##### ***Randomization***

Randomization will occur in during the pre-operative consult although the participant's final eligibility will be determined during surgery (see section on Eligibility). Patients will be randomized to undergo either ADM assisted one-stage reconstruction or two-stage reconstruction with TE placement without the use of ADM. The randomization allocation list will be developed by the Department of Epidemiology and Biostatistics at the University Health Network Research Institute. Sequentially numbered and sealed envelopes containing the treatment assignments will be prepared and given to the study coordinator in charge of the study site. Each envelope will contain two identical datasheets with the patient's name, medical record number and treatment assignment. One sheet will be returned to the study coordinator and the other sheet will be placed in the patient's chart.

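### Randomized patients can be ruled ineligible in surgery with the arm on file, and section 9b does not say they stay in the analysis; the likely bias is small

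*Combined protocol and SAP*

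**What the plan says.** - **Order of events.** The Randomization section places randomization at the pre-operative consult and notes that the participant's "final eligibility will be determined during surgery". The eligibility section agrees: "Following randomization preoperatively, eligibility will be determined once more intraoperatively".
- **Criteria applied in surgery.** One concerns the axillary procedure. The other excludes "Patients who have significant mastectomy flap ischemia or asymmetry between the two sides". No grading, threshold or independent assessor is given for the second. On numbers, the plan says: "It is anticipated that less than 5% of patients will be deemed ineligible on the basis of these 2 intra-operative exclusion criteria".
- **Who can know the arm.** "Sequentially numbered and sealed envelopes containing the treatment assignments will be prepared", but once the envelope is opened one datasheet goes to the coordinator and "the other sheet will be placed in the patient's chart". No step hides the arm from the person making the intra-operative decision.
- **Registration and accrual (iib-1. Study Design).** "After obtaining informed consent and confirming eligibility both pre- and intra-operatively, patients will be registered in the study". The target is: "Patients will be enrolled until there are 72 evaluable patients enrolled in each study arm". Evaluable is not defined.
- **Analysis set (9b. Intention to treat analysis).** Patients who abandon reconstruction, or whose expander or implant is removed early, stay in. Patients ruled ineligible during surgery are not mentioned.
- **Progress (iia-3. Preliminary Data).** 67 women are registered, 51 of them randomized (27 one-stage, 24 two-stage) and 16 still waiting.

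**The concern.** An exclusion made after randomization, on a judgement, by someone who can know the arm, is no longer protected by the randomization. If the excluded patients also leave the analysis, the arms may differ in flap quality for reasons other than chance.

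The plan offers a plausible route to uneven exclusion. In Group A the permanent implant goes in at once; in Group B the expander is inflated only as far as the skin flap allows without strain. A surgeon might tolerate a marginal flap differently in the two settings. The documents do not say that this happens.

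Short-term complications are the outcome most exposed. If marginal flaps were removed more often from the one-stage arm, that arm's complication rate would look lower, and the secondary hypothesis of no increase with ADM would be easier to support. Breast Q is less exposed, because a few patients move a mean on a 100-point scale very little.

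**Working it through.** **1. The plan's sample size.** Inputs from iib-10: difference 10, SD 20, alpha 0.05 (taken as two-sided), power 85%. n per arm = 2 × (1.960 + 1.036)² × 20² / 10² = 71.8, so 72. This reproduces the plan. The t-based power at 72 per arm is 84.6%.

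**2. How many patients.** 5% of 144 = 7.2, about 7, for all intra-operative exclusions together; the flap criterion accounts for only part. To finish with 72 per arm after a 5% loss, 72/0.95 = 75.8, so 76 per arm are randomized.

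**3. What the interim rates show.** The reported events are 2 minor in the one-stage arm, and 3 minor and 1 major in the two-stage arm.

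| Arm | All randomized | One fewer | Reported |
|---|---|---|---|
| One-stage, minor | 2/27 = 7.4% | 2/26 = 7.7% | 7% |
| Two-stage, minor | 3/24 = 12.5% | 3/23 = 13.0% | 12.5% |
| Two-stage, major | 1/24 = 4.2% | 1/23 = 4.3% | 4% |

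The denominators are therefore all 51 listed as randomized, and no exclusion is visible among them. Patients removed earlier may simply not be listed. Even a true 0/51 has a one-sided 95% upper bound of 1 − 0.05^(1/51) = 5.7%, so it does not rule out 5%.

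**4. Effect on complications (illustration).** Assume no true difference, a rate of 6/51 = 11.8% in both arms (pooled interim, one event per patient), 76 randomized per arm, and flap exclusions of 3 in one arm and 1 in the other. With k excluded, of whom a share f would have had a complication, the rate in those retained is (76 × 0.1176 − k × f)/(76 − k), where 76 × 0.1176 = 8.94.

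| f | 3 excluded | 1 excluded | False difference |
|---|---|---|---|
| 0.118 (like everyone else) | 11.8% | 11.8% | 0 |
| 0.30 | 8.04/73 = 11.0% | 8.64/75 = 11.5% | 0.5 points |
| 0.50 | 7.44/73 = 10.2% | 8.44/75 = 11.3% | 1.1 points |
| 1.00 | 5.94/73 = 8.1% | 7.94/75 = 10.6% | 2.4 points |

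Sampling SE of the difference = √(2 × 0.1176 × 0.8824/76) = 5.2 points, so the false difference is about 0.1 to 0.5 SE. Equal numbers of similar patients excluded from both arms give 0 at any f.

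**5. Effect on Breast Q.** Shift = (difference in k)/76 × deficit of the excluded patients. For an assumed deficit of 10 to 20 points: 2/76 × 10 = 0.3 and 2/76 × 20 = 0.5, against a target of 10.

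**6. Price of keeping everyone.** If 5% of each arm contribute no arm difference, the 10-point target becomes 0.95 × 10 = 9.5. Power with 72 per arm providing data is then 80.8%, against 84.6%. With 80 per arm it is 84.8%.

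**The case against.** The strongest reply is that removal is inferred from silence. Section 9b invokes intention to treat and names two groups who stay; it does not say that others go. A patient whose reconstruction is not carried out might count as having abandoned it. Evaluable could simply mean having questionnaire data. The registration order in iib-1 is also weak evidence of removal, because iia-3 counts 16 registered women not yet randomized, so that order was evidently not followed.

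Much of this stands. A reader might infer that the plan drops and replaces these patients as a stated rule; it does not say so. The ambiguity remains, however. The abandonment clause does not clearly cover them: a patient can fail the axillary criterion and still complete reconstruction. As 9b is written, an analyst could settle the question after seeing results by arm.

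Two other stronger readings also fail:

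- **That the interim figures settle the matter.** They cannot separate no exclusions, exclusions that were kept, and exclusions never listed among the 51.
- **That the bias could be large.** A split such as 5 v 2 would spend the whole allowance of about 7 on the flap criterion and leave nothing for the axillary one. Uneven exclusion by arm is not documented, and neither is any complication risk for those excluded.

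**Conclusion.** The point holds as a gap in the definition of the analysis set, with a small likely effect. Randomization before the final check, the unthresholded flap criterion, the assignment in the chart and the limited wording of 9b are all in the text. That excluded patients leave the analysis is the most natural joint reading of these sections, but it is not stated.

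On the plan's own anticipation, bias in the complication comparison would probably be about half a point to two and a half points, well inside sampling error, and under 1 point on Breast Q. This rests on three assumptions: the 5% expectation is met, the flap exclusions split about 3 v 1, and 30% to 100% of those excluded would have had a complication. Severity is minor to should-fix. It deserves action because the correction is cheap and removes a choice that could otherwise be made after the data are seen.

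**What to change.** 1. **Analysis set.** In 9b, define the ITT set as every randomized patient, including those ruled ineligible in surgery, analysed by assigned arm for Breast Q and complications. Use the intra-operatively eligible set only as a sensitivity analysis.
2. **Assessment times.** Keep the planned times for all who complete reconstruction. For patients with no completion date, including those whom 9b already retains after abandonment, prespecify one fallback time, identical in both arms. The 2-week Breast Q and short-term complications are already timed from surgery and need no change.
3. **Accrual.** Define evaluable as having primary-outcome data, and let the term govern accrual only.
4. **Reporting.** Give intra-operative exclusions by arm and by criterion, including any among, or removed before the count of, the 51 randomized.
5. **Registration.** Reconcile iib-1, which registers after the intra-operative check, with iia-3, which counts registered women awaiting randomization.

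The cost is follow-up of about 7 more patients, some SAP wording and slight dilution. The plan should state that, if 5% of each arm contribute no difference, power with 72 per arm providing data is about 81% rather than 85%; about 80 per arm with data would restore it. Keeping the arm concealed until the intra-operative decision is recorded would be a further safeguard, but it is optional: theatre would have to be ready for either operation, and it cannot reach the 51 already randomized.

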#### ***Intra-operative eligibility:***

#### Subject Inclusion Criteria

- Patients who undergo sentinel lymph node biopsy without completion axillary lymph node dissection

#### Subject Exclusion Criteria

- Patients who undergo therapeutic or completion axillary lymph node biopsy
- Patients who have significant mastectomy flap ischemia or asymmetry between the two sides

If a completion or therapeutic axillary lymph node dissection is performed at the time of mastectomy, then the likelihood of the patient requiring postmastectomy radiation will be quite significant. It is anticipated that less than 5% of patients will be deemed ineligible on the basis of these 2 intra-operative exclusion criteria.

#### iib-4. Intervention plan

##### ***Pre-intervention Evaluation***

During the pre-operative consultation, written informed consent will be obtained from patients who meet the inclusion and exclusion criteria and who are willing to participate. (APPENDIX 3)

##### ***Randomization***

Randomization will occur in during the pre-operative consult although the participant's final eligibility will be determined during surgery (see section on Eligibility). Patients will be randomized to undergo either ADM assisted one-stage reconstruction or two-stage reconstruction with TE placement without the use of ADM. The randomization allocation list will be developed by the Department of Epidemiology and Biostatistics at the University Health Network Research Institute. Sequentially numbered and sealed envelopes containing the treatment assignments will be prepared and given to the study coordinator in charge of the study site. Each envelope will contain two identical datasheets with the patient's name, medical record number and treatment assignment. One sheet will be returned to the study coordinator and the other sheet will be placed in the patient's chart.

### ***Group A: Experimental Treatment***

In **Group A**, the experimental group, the plastic surgeon will create the breast pocket which will involve the use of an implantable layer of ADM. Pocket dissection will begin with elevation of the pectoralis major muscle. ADM will be used to create the infero-medial pocket thereby eliminating the need for surgical elevation of the anterior rectus fascia as well as the serratus musculature/fascia. It will be secured to the lateral border of the pectoralis major using absorbable sutures. Inferiorly, it will be sutured to the anterior rectus fascia along the base of the implant pocket. Laterally, it will be sutured to the serratus fascia in the line of the anterior axillary fold. A permanent anatomic cohesive silicone gel (Style 410, Allergan, Santa Barbara, CA) will be placed in the pocket and complete closure of the pocket will be performed using an absorbable suture. Two drains will be placed in the breast pocket, one deep to ADM and one on the superficial surface of ADM at the inferior mastectomy gutter.

### ***Group B: Standard Treatment***

In **Group B**, the standard treatment group, the tissue expander pocket will be made by elevating the pectoralis major muscle, serratus anterior muscle/fascia laterally and rectus fascia inferiorly. An anatomic-shaped tissue expander (Allergan, Santa Barbara, CA) will be placed beneath the muscle-fascial pocket and pocket will be closed using an absorbable suture. Sterile injectable saline will be used to inflate the tissue expander until an adequate volume without tension on the mastectomy skin flap is achieved. In this case, only one drain will be placed deep to the mastectomy skin flaps. All patients will receive standard peri-operative antibiotics.

#### **iib-5. Interventional agent**

ADM derived from cadaveric human skin tissue is supplied by US AATB-compliant tissue banks utilizing the standards of the American Association of Tissue Banks (AATB) and Food and Drug Administration's (FDA) guidelines. We will use AlloDerm (6 x 12cm) labeled "Thick". We have no financial or other conflicts of interest to report for LifeCell corporation. The tissue substitute will be stored under refrigeration at 1°C -10°C (34-50°F) as recommended by the product insert. AlloDerm will be opened and placed on the operating room table in a sterile fashion, and soaked in sterile water for a minimum of 20 minutes before implantation.

#### **iib-6. Postoperative treatment**

In **Group B**, at 2 weeks after the operation, office expansion will be undertaken and continued on a biweekly basis. With each expansion, the endpoint of expansion will include either: (1) persistent blanching or congestion of the mastectomy flap; or, (2) patient discomfort. The expansion phase will be considered complete once the volume in the expanded breast represents 100 percent (+/- 20 percent) of the recommended expander volume. If required, postoperative chemotherapy is generally given during the expansion period. Expanders are then exchanged approximately between 4-6 weeks following the completion of chemotherapy or 3-6 months following completion of inflation. All patients in group B will undergo a second exchange procedure at which time the expander is removed and a permanent implant is placed. In all instances, the permanent implant to be used will be anatomic cohesive silicone gel implants (Style 410, Allergan, Santa Barbara, CA).

#### **iib-7. Confounders and their Measurements**

Critical covariates will be identified at baseline and documented in the demographic assessment forms. These confounders can be conceptually divided into procedure specific, patient specific, and disease specific confounders. Analysis will be adjusted for the confounders using both stratification and multivariate regression. (see section on Outcome and their measurements) Stratified randomization is

performed based on laterality of the reconstruction (unilateral vs. bilateral) and study site. Other procedure specific confounders include skin-sparing vs. nipple-sparing mastectomy and the primary reconstructive surgeon. The patient specific confounders will include age, body mass index; socioeconomic status assessed using proxy measures of income and highest obtained level of education and marital status. Co-morbidities will be categorized as having one or more the following possible chronic conditions (emphysema, heart disease, diabetes, hypertension, stroke, arthritis, or other chronic condition). The disease specific confounders will include stage of breast cancer and present or past chemotherapy treatment.

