## **iib-9. Data Analysis**

### **9a. Confounders and their Measurements**

Critical covariates will be identified at baseline and documented in the demographic assessment forms. (APPENDIX 7) Analysis will be adjusted for the confounders using both stratification and controlled for during repeated measures analysis using SPSS v18.

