### **iib-10. Sample Size**

We consider clinically relevant change in the quality of life as a difference that exceeds half a standard deviation of the baseline value. Field-testing data of the Breast Q $\odot$  has found that the standard deviation of both the psychosocial function and satisfaction distributions is approximately 20. Thus, the minimum significant difference of score in each subscale is calculated to be 10. When we set our power at 85% with a  $\beta$  error of 0.1 and a standard  $\alpha$  error rate of 0.05, and applied the equation for equal sample sizes, we calculated a **minimum sample size of 72 patients per arm** for a total sample size of 144 patients. This sample size is also sufficient with power 84%,  $\alpha$  0.05, to detect a value of 0.06 for  $\eta^2$ , representing a medium effect size of the proportion of variability in the outcome variable (Breast Q $\odot$ ) that is explained by the independent variable(s), e.g., intervention.

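### The Breast Q analysis is committed to about 12 loosely defined covariates that omit the pre-operative score, and the sample size makes no allowance for them; a power loss is possible but not shown

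*Combined protocol and SAP*

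**What the plan says.** Section iib-7 groups the confounders as procedure, patient and disease specific. Counting them gives 12: site, laterality, mastectomy type, primary surgeon, age, body mass index, income, education, marital status, co-morbidity, cancer stage and chemotherapy. The socioeconomic items read "socioeconomic status assessed using proxy measures of income and highest obtained level of education and marital status". The commitment is general: "Analysis will be adjusted for the confounders using both stratification and multivariate regression". Section 9a, within Data Analysis, says: "Analysis will be adjusted for the confounders using both stratification and controlled for during repeated measures analysis using SPSS v18".

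Section 9c i) describes the primary analysis as a repeated measures comparison of the two Breast Q domain scores before surgery and at three follow-ups. It names no covariate. Section 9c ii) compares complications by Pearson chi-square or binomial test and contracture grade by Pearson chi-square. Section 9c iii) puts an unspecified vector of confounders into the net benefit regression.

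Section iib-10 takes it that "the standard deviation of both the psychosocial function and satisfaction distributions is approximately 20" and that "the minimum significant difference of score in each subscale is calculated to be 10", and arrives at a "minimum sample size of 72 patients per arm". It contains no covariate term.

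**The concern.** In a randomized trial the listed variables differ between arms only by chance, so adjustment is worth its cost only if they predict the outcome. Each uninformative parameter uses a degree of freedom and inflates the variance of the treatment estimate through chance imbalance. The variable one would most expect to predict a later Breast Q score is the earlier one, and it is absent from the list.

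Three further matters do not depend on prognostic strength.

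- **Undefined model.** Coding, selection and the treatment of surgeon (fixed or random) are open, so several primary models could be fitted after the data are seen.
- **Missing covariates.** In a complete-case fit, a woman lacking any one covariate leaves the analysis. That sits badly with the intention-to-treat commitment in 9b.
- **Timing.** Randomization takes place at the pre-operative consult. The chemotherapy item covers current or previous treatment without a date, while iib-6 expects postoperative chemotherapy, where needed, generally during expansion. Section iib-7 says covariates are identified at baseline, but does not clearly exclude later values.

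**Working it through.** **Plan's own figure.** Inputs from iib-10: difference 10, SD 20, alpha 0.05 (taken as two-sided), power 85%.

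n per arm = 2 × (1.960 + 1.036)² × 20² / 10² = 71.8, so 72. The figure reproduces. The same sentence in iib-10 also gives a beta error of 0.1, which would be 90% power and need 85 per arm; 72 matches 85%.

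**Parameter count.** The documents give no category levels, and surgeon numbers only for Vancouver (three). Assumed: site 2, laterality 1, mastectomy type 1, surgeon within site 3–5, age 1, body mass index 1, income 2–4, education 2–3, marital status 1–3, co-morbidity 1, stage 3–4, chemotherapy 1. Total 19 to 27. Site plus surgeon (5–7 contrasts) corresponds to 6–8 surgeons overall.

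**Power at one time point with p covariate parameters.** R² is the share of outcome variance that they explain.

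- df = 144 − 2 − p
- variance inflation = (144 − 3)/(144 − p − 3), taken as 1 when p = 0
- SE = 20 × √(1 − R²) × √(4/144) × √inflation
- power from the noncentral t with noncentrality 10/SE, two-sided 5%

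At R² = 0:

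| p | Inflation | SE | 10/SE | Power |
|---|---|---|---|---|
| 0 | 1 | 3.333 | 3.00 | 84.6% |
| 4 (site, laterality, baseline score) | 141/137 = 1.029 | 3.382 | 2.96 | 83.6% |
| 12 (one per covariate) | 141/129 = 1.093 | 3.485 | 2.87 | 81.3% |
| 19 | 141/122 = 1.156 | 3.583 | 2.79 | 79.1% |
| 27 | 141/114 = 1.237 | 3.707 | 2.70 | 76.3% |

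Simulation by ordinary least squares (8,000 runs per setting) agrees: about 79% at 19 parameters and 76–77% at 27.

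With prognostic covariates:

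| R² | 19 parameters | 27 parameters |
|---|---|---|
| 0.10 | 83.1% | 80.5% |
| 0.20 | 87.2% | 84.9% |
| 0.30 | 91.1% | 89.2% |

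Break-even with the unadjusted test is at R² of 13.7% (19 parameters) and 19.4% (27).

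**Comparison with a short list.** Take 4 parameters (site 2, laterality 1, baseline score 1) against the full list plus baseline score, 20 to 28 parameters. The longer model breaks even when the added variables explain about (20 − 4)/137 = 12% to (28 − 4)/137 = 18% of the variance left by the short list.

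**Missing covariates.** The rates are assumptions. If each of 12 covariates is independently missing in 2–3% of women, 0.98¹² = 78% to 0.97¹² = 69% have complete data (113 to 100 of 144). If only four are at risk, such as income, education, marital status and body mass index, 0.98⁴ = 92% to 0.97⁴ = 89% are complete (133 to 127 of 144).

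**The case against.** The strongest reply is that adjustment may help. The documents give no R² for the listed covariates. Above about 14–19% the full list gains power, so a reader who infers that the stated 85% falls to the upper 70s is taking the worst case as the result. This stands.

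The parameter count is also assumed. The demographic form is an appendix that is not available here, and with one parameter per covariate the worst case is 81.3%. Against a short list rather than no adjustment, the worst-case loss is smaller too, because the short list itself costs about one point at R² = 0. The calculation uses one time point, whereas 9c plans repeated measures, so it cannot say what power the planned analysis has. All of this stands.

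Nor is the pre-operative score ignored: 9c includes it as one of the time points. The point is only that it is not an adjustment variable. What the reply leaves untouched is that the model is undefined and the sample size silent on it.

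A reader might also infer from the general sentence in iib-7 that complications will be modelled on the full list, and that this analysis is invalid. The interim short-term rate, (2 + 4)/(27 + 24) = 6/51, scales to 16.9 events in 144 women, or 0.6 to 0.9 per parameter, and such a model would be unstable. But 9c ii) plans chi-square or binomial tests, 9a places the adjustment in the repeated measures analysis, and no section specifies a logistic model. The 16.9 also omits complications later than two months. What remains is wording in iib-7 and 9c ii) that has not been reconciled.

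**Conclusion.** The concern holds as a defect of specification. Sections iib-7 and 9a commit the Breast Q analysis to about 12 covariates without coding, selection or missing-data rules, leave out the collected pre-operative score, and have no counterpart in iib-10.

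The possible cost is about 5.5 to 8 percentage points at one time point (84.6% to 79.1% or 76.3%), conditional on 19 to 27 parameters and no prognostic value. It is zero at about 14–19% of variance explained and becomes a gain beyond that. The documents do not show which case applies, so no net loss of power is established. Nor do they support calling the planned complication tests invalid. The exposure to missing covariates and the undated chemotherapy item are real, but their size cannot be fixed from the documents.

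**What to change.** In iib-7 and 9a, define one primary Breast Q model with arm, site, laterality and the pre-operative Breast Q score. Because 9c currently treats that score as a time point, say there that the three post-operative scores are the outcomes once it becomes a covariate. Move the remaining listed variables to one labelled sensitivity analysis, using only values fixed before randomization, with their coding, the treatment of surgeon and the handling of missing values stated.

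Reconcile iib-7 with 9c ii) by stating that complications and contracture are not adjusted for the full list and are at most stratified by site and laterality.

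The cost is wording only; the baseline score is already collected and site and laterality already stratify randomization. The downside is some lost precision if the moved variables explain more than roughly 12–18% of the variance left by the short list. The sensitivity analysis would show this.

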### **Stratification**

Stratified randomization will be performed based on two a priori factors that can influence outcome: unilateral vs. bilateral reconstruction, and study site. (Study Schema diagram) It is well documented in the literature that aesthetic outcomes tend to be superior in bilateral reconstructions than unilateral cases. In addition, patients will be stratified by the study site as there may be significant differences in patient characteristics for each individual hospital catchment area.

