### **9c. Measurement of the Primary Objective:**

#### ***i) Primary Analysis***

Each of the two domain-specific summary scores on function and satisfaction will be transformed on a scale from 0 to 100 using RUMM software. Mean scores and standard deviation for each surgery group will be calculated and compared. To address our primary aim of comparing patient satisfaction and quality of life between **Group 1** (one-stage with ADM) and **Group 2** (two-stage group without ADM) before and at the three post mastectomy follow up reference time points, we will use the **repeated measure analysis** to examine the time effect and time-group interaction. In all analyses, statistical significance will be designated at  $p <= 0.05$  level.

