#### ***ii) Secondary Analysis***

Short-term (intra-operative and early post-operative) and long-term postoperative complications will be documented and collected prospectively at each site by the study coordinator. Group comparisons will be performed using the Pearson's chi-square test or binomial test, where appropriate for these categorical variables. Repeated measure analysis will be used for Breast Aesthetic Score at 6 and 12 months post mastectomy. The Modified Baker Scale for capsular contracture results in an ordinal variable which will be compared using the Pearson's chi-square test.

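### The complication and Baker-grade tests leave out site and laterality, although randomization is stratified by both and the plan promises adjusted analyses

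*Combined protocol and SAP*

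**What the plan says.** All references are to the combined protocol and SAP.

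- **Randomization.** Section 9a, Stratification: "Stratified randomization will be performed based on two a priori factors that can influence outcome: unilateral vs. bilateral reconstruction, and study site". The Preliminary Data section adds that blocks of eight are used. With three sites and two laterality levels there are six strata.
- **Promise of adjustment.** Section iib-7: "Analysis will be adjusted for the confounders using both stratification and multivariate regression". It names laterality and site first and then moves on to other confounders. Section 9a repeats the promise and says that confounders will be controlled for in the repeated-measures analysis.
- **Primary analysis, 9c i).** "Mean scores and standard deviation for each surgery group will be calculated and compared", followed by a repeated-measures analysis of the time effect and the time-by-group interaction. No covariates are listed.
- **Secondary analysis, 9c ii).** For complications, "Group comparisons will be performed using the" Pearson chi-square or a binomial test. Baker grade, which the plan itself calls ordinal, also gets a Pearson chi-square. The aesthetic score gets a repeated-measures analysis. No strata appear.
- **Hypothesis on complications (Specific Aims).** ADM in one stage does not raise short- or long-term complications.

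**The concern.** Blocked randomization within prognostic strata balances the arms on those strata, so the true variance of the treatment contrast falls. A test that ignores the strata still counts the between-stratum variation as noise. Its standard error is then larger than it should be, and its true size is below the nominal 5%.

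For most endpoints a slightly conservative test is only a small waste. For complications it has a direction: the trial hopes to find no increase, and a test with too little sensitivity makes that finding easier to reach. The plan also contradicts itself here, because iib-7 promises an adjustment that the tests in 9c ii) cannot deliver.

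**Working it through.** **1. Which analyses can carry the strata as written?**

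| Analysis | Method in 9c | General promise to adjust applies? | Site and laterality named? |
|---|---|---|---|
| Breast Q | Repeated measures | Yes (iib-7, 9a) | No |
| Aesthetic score | Repeated measures | Yes (iib-7, 9a) | No |
| Net benefit | Regression with a vector of confounders | Yes | No, members not listed |
| Complications | Pearson chi-square or binomial | Promised in iib-7, but the test takes no covariates | No |
| Baker grade | Pearson chi-square | Promised in iib-7, but the test takes no covariates | No |

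The conflict is in the last two rows. The first three are under-specified, not contradictory.

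**2. Direction for a binary outcome.** Let p_s be the complication rate in stratum s and p the overall rate. Then p(1−p) = average of p_s(1−p_s) + variance of p_s between strata. Pearson's test uses the left side. With balance inside strata, the relevant variance is the first term on the right. The test is therefore conservative whenever the p_s differ, and correct when they do not. The documents give no p_s, so the size cannot be computed.

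**3. The plan's own sample size.** Inputs from section iib-10 are difference 10 ("the minimum significant difference of score in each subscale is calculated to be 10"), SD 20, α 0.05 and power 85%. Two-sided testing is an assumption, since sidedness is not stated.

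n = 2 × (1.960 + 1.036)² × 20² / 10² = 71.8, so 72 per arm. This reproduces the plan. The same sentence also gives a β of 0.1, which would need 85 per arm; that is a separate matter.

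The calculation uses the total SD of 20, so planned power takes no credit for adjustment.

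**4. Guide to size for a continuous outcome at one time point.** R² is the share of variance explained by site and laterality. It is assumed, because the documents give none.

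- Unadjusted SE = 20 × √(2/72) = 3.33
- Adjusted SE = 3.33 × √(1−R²)
- True size of the unadjusted test = 2 × [1 − Φ(1.96/√(1−R²))]
- Adjusted power = Φ(10/adjusted SE − 1.96)
- Unadjusted power at the same R² = Φ((10 − 1.96 × 3.33)/adjusted SE)

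| R² | Adjusted SE | Unadjusted SE too large by | True size | Power unadjusted | Power adjusted | Gain (points) |
|---|---|---|---|---|---|---|
| 0 | 3.33 | 0% | 0.050 | 85.1% | 85.1% | 0 |
| 0.05 | 3.25 | 2.6% | 0.044 | 85.7% | 86.8% | 1.1 |
| 0.10 | 3.16 | 5.4% | 0.039 | 86.4% | 88.5% | 2.2 |
| 0.15 | 3.07 | 8.5% | 0.034 | 87.0% | 90.2% | 3.2 |

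Gains are taken before rounding. A simulation with six strata, blocks of eight and N = 144 (6,000 runs per setting, assumed stratum shares and effects) agrees. At R² = 0.10, rejection under the null was 0.042 unadjusted and 0.051 adjusted, and power was 85.3% and 87.7%.

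These power figures do not carry over to the complication or Baker-grade tests.

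**5. How sparse are the strata?** In the Preliminary Data, Women's College unilateral has 2 patients per arm. The interim report gives 2 events in the one-stage arm (2/27 = 7%) and 4 in the two-stage arm (3/24 = 12.5% minor, 1/24 = 4% major). With so few events, some strata may have none.

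**The case against.** The strongest reply is that the plan already commits to adjustment. Section 9a says confounders are controlled for in the repeated-measures analysis, and iib-7 reads most naturally as counting site and laterality among them. This stands for the Breast Q and the aesthetic score. A reader might infer from 9c i) alone that the primary test ignores the strata and that its standard error is too large. The documents do not support that: what is missing there is an explicit list of terms. The list is still worth having, since iib-7 offers about a dozen candidates without priority, including surgeon, which may overlap with site.

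Three further replies have weight.

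- The primary test is of change over time. A stratum effect that is constant over time cancels from the time-by-group interaction, so the table in the working does not describe that test, and adding main effects alone would not alter it.
- The evidence that the strata are prognostic is thin. The literature cited in 9a concerns laterality and aesthetic results. For site the plan says only that patient characteristics may differ. Nothing is said about complications.
- Stratified tests have their own cost with rare events, because strata without events contribute nothing.

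None of this rescues 9c ii). One could argue that the word stratification in iib-7 already implies stratified tests, but the only stratification the plan describes is of the randomization, and the tests it names are unstratified.

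**Conclusion.** The point holds for complications and Baker grade. Their tests cannot include the factors by which the trial randomizes, and they conflict with iib-7. If the strata are prognostic, the tests are somewhat conservative. For complications that leans towards the hypothesis of no increase. If the strata are not prognostic, nothing is lost.

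The size is unknown. The 1.1 to 3.2 power points are a guide for a continuous outcome at one time point, under assumed R² values of 0.05 to 0.15 and two-sided testing. A reader might measure the gain from the fixed planning power of about 85% and arrive at a larger figure. That comparison is not like with like, because balanced prognostic strata also raise the power of the unadjusted test.

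A reader might also infer bias or an inflated type I error. Neither follows, since the error is in the conservative direction. Planned power for the primary outcome does not depend on adjustment.

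**What to change.** 1. In 9c ii), replace the plain tests for complications with a Cochran-Mantel-Haenszel test stratified by site (three levels) and laterality (two levels). Specify an exact version in advance for rare events.
2. For Baker grade, use a stratified ordinal test, for example van Elteren, or ordinal regression with both factors.
3. In 9c i), and for the aesthetic score in 9c ii), name site and laterality as fixed terms in the repeated-measures models. If the time-by-group interaction is the test of interest, include their interactions with time as well. This makes 9c agree with iib-7 and 9a.

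The cost is SAP wording. Both factors are known for every randomized woman because they define the strata, so no new data or patients are needed. The one downside is sparse strata, which the exact test in item 1 addresses.
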